9.2 Sample Size/Accrual Rate

Planned sample size: 10-30 patients

As this is a phase 1 study, the sample size will be determined by the number of patients required to establish the MTD of IPdR given with capecitabine and RT. The statistical power of the correlative analyses with samples sizes of up to 30 patients is presented in Section 9.4.1.

Estimated patient accrual rate:

- Part IA: The accelerated titration design with single-patient cohorts will allow for an estimated patient accrual rate of 1 patient every 3 months.
- Part IB: Up to 3 patients at a time may be treated at a given dose level, allowing for an estimated patient accrual rate of 2-3 patients every 3 months.

PLANNED ENROLLMENT REPORT

Racial Categories	Ethnic Categories				Total
	Not Hispanic or Latino		Hispanic or Latino		
	Female	Male	Female	Male	
American Indian/ Alaska Native	0	0	0	0	0
Asian	1	1	0	0	2
Native Hawaiian or Other Pacific Islander	0	0	0	0	0
Black or African American	3	3	0	0	6
White	5	5	3	3	16
More Than One Race	2	2	1	1	6
Total	11	11	4	4	30

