- a “moderate” toxicity, two additional patients will be entered at this dose level, and if
 - one of these patients develops a DLT, the stop/switch rule is invoked, and part IB commences
 - one of these patients develops a “moderate” toxicity, the stop/switch rule is invoked, and part IB commences
 - neither of the two additional patients develops a DLT or “moderate” toxicity, part IA recommences at the next dose level

A patient will be considered unevaluable if they receive $<67\%$ of their total intended dose of any study treatment (IPdR, capecitabine, or RT) for non-protocol required reasons. Patient medication diaries and RT documentation will be reviewed as each patient comes off-study to determine the actual total doses of each study treatment they received. If a patient is deemed unevaluable by this definition, they will be replaced by a new patient to be treated at the same intended dose level.

Part IA dose escalation schema			
Dose Level	Total radiation Gy (45 Gy primary field, 5.4 Gy [contact] Gy/fraction/day)	Capecitabine (mg/m² BID)	IPdR (mg BID) Administered throughout radiation
1A	50.4	825 mg/m ² BID	75 mg BID
2A	50.4	825 mg/m ² BID	150 mg BID
3A	50.4	825 mg/m ² BID	300 mg BID
4A	50.4	825 mg/m ² BID	600 mg BID
5A	50.4	825 mg/m ² BID	1,200 mg BID

BID – Twice Daily, RT – Radiation therapy

Part IA is closed to further accrual.

Part IB:

Under Part IB of this protocol, cohorts of 3-6 patients will be entered per dose level. In Part IB, 3 patients will initially be accrued to a dose level. If 0 of 3 patients do not experience grade 3 non-hematopoietic or grade 4 hematopoietic/GI DLT, then dose escalation will proceed. If a DLT is observed in one of the first 3 patients in a dose level cohort, the cohort will be expanded to a maximum of 6 patients.

Part IB dose escalation schema			
Dose Level	Total radiation Gy (45 Gy primary field, 5.4 Gy [contact] Gy/fraction/day)	Capecitabine (mg/m² BID)	IPdR (mg QD) Administered throughout radiation^{1,2}
1B	50.4	825 mg/m ² BID	75mg QD
2B	50.4	825 mg/m ² BID	150mg QD
3B	50.4	825 mg/m ² BID	300mg QD
4B	50.4	825 mg/m ² BID	600mg QD
5B	50.4	825 mg/m ² BID	1200mg QD
6B	50.4	825 mg/m ² BID	1800mg QD
7B	50.4	825 mg/m ² BID	2400mg QD

QD – Once Daily, BID – Twice Daily, RT – Radiation therapy

¹ The maximum allowed dose of IPdR is 2,400mg QD

² Actual doses will be rounded to account for availability of only 75 mg and 600 mg IPdR capsules

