6.2 Definition of Dose-Limiting Toxicity

Management and dose modifications associated with the above AEs are outlined in Section 7.

DLTs will be captured until 4 weeks after completion of IPdR therapy and will be graded according to the CTCAE v5.0. DLTs will be defined as clinically significant grade 3 or 4 toxicities possibly or probably related to study treatment.

- Grade 4 neutropenia (ANC < 500/mm³)
- Grade 4 electrolyte toxicities
- ANC <1000/mm³ with fever (temp >101 F) or infection
- Grade 4 thrombocytopenia: Platelets <25,000/mm³
- Platelets <50,000/mm³ requiring transfusion
- Grade 3 or 4 treatment related non-hematologic toxicities excluding alopecia.
- Patients who receive <67% of intended IPdR secondary to treatment related toxicities will also be considered as having a DLT

In addition, during chemoradiation, DLTs will also include AEs requiring interruptions of radiation for >5 consecutive scheduled fractions (and / or ≥ 9 total scheduled fractions) or for >10 consecutive scheduled doses of capecitabine (and / or ≥ 19 total scheduled doses of capecitabine). The following AEs will not be considered DLTs:

- Any grade of alopecia,
- Grade 3 arthralgia or myalgia,
- Brief (<1 week) grade 3 fatigue,
- Grade 3 fever,

- Grade 3 diarrhea or vomiting responding to supportive care
 - Grade 3 nausea, vomiting or diarrhea will be considered a DLT if it occurs for greater than 48 hours despite maximal medical support.
- Grade 3 radiation dermatitis,
- Grade 3 or 4 electrolyte abnormalities will not be considered DLTs if the electrolyte disorder can be corrected to grade 2 or less within 72 hours.

All patients who have received at least one dose of IPdR are evaluable for toxicities.

For dose escalation decisions, patients should have completed $\geq 80\%$ of the planned chemoradiation doses unless the reason for discontinuation is an AE that qualifies for DLT.

Dose escalation will proceed within each cohort in Part IB according to the following scheme. DLT is defined above.

Number of Patients with DLT at a Given Dose Level	Escalation Decision Rule
0 out of 3	Enter 3 patients at the next dose level.
≥ 2	Dose escalation will be stopped.

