1 out of 3	Enter 3 more patients at this dose level. 
• If 0 of these 3 patients experience DLT, proceed to the next dose level.• If 1 or more of this group suffer DLT (i.e. 2 of 6 patients), then dose escalation is stopped, and this dose is declared the maximally administered dose.
≤ 1 out of 6 at highest dose level below the maximally administered dose	This is generally the recommended phase 2 dose. At least 6 patients must be entered at the recommended phase 2 dose.

During the MTD dose finding portion, patients who are removed from study for reasons other than a DLT will be replaced.

6.3 Dose Expansion Cohorts:

For the expansion cohort, patients will continue to be monitored for occurrence of DLT. Three additional patients will be treated at the dose level below the dose associated with DLT to establish the MTD. The MTD is defined as the dose below which 2 or more of 3 to 6 patients experience DLT. The MTD will be deemed to be RP2D if $\geq 80\%$ of the patients are able to receive $\geq 80\%$ of the planned treatment doses. Monitoring of all safety and toxicity data is done by the Principal Investigator and the Corresponding Organization on a real-time basis as data are entered into Medidata Rave using the Web Reporting Module. All participating sites are expected to notify the Principal Investigator when a DLT has occurred.

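### The planned 10–30 patients is not derived from the current seven-level Part IB and may not be enough to complete the escalation rule

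*Combined protocol and SAP*

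**What the plan says.** Section 9.2 states "Planned sample size: 10-30 patients". It adds that "the sample size will be determined by the number of patients required to establish the MTD of IPdR given with capecitabine and RT", but shows no calculation for 10 or for 30. The figure of 30 appears twice more in that section: as the total of the planned enrolment table, and in the sentence "The statistical power of the correlative analyses with samples sizes of up to 30 patients is presented in Section 9.4.1".

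The escalation rules are elsewhere:

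- Section 6.1.1: "Under Part IB of this protocol, cohorts of 3-6 patients will be entered per dose level". The Part IB schema lists seven levels, 1B to 7B, with this limit on the top one: "The maximum allowed dose of IPdR is 2,400mg QD".
- Section 6.2: after no DLT in three patients, the instruction is "Enter 3 patients at the next dose level".
- Sections 6.1.1 and 6.2: after one DLT in three, "the cohort will be expanded to a maximum of 6 patients". Escalation resumes if none of the added three has a DLT.
- Section 6.2: "At least 6 patients must be entered at the recommended phase 2 dose". During dose finding, patients removed for reasons other than a DLT are replaced.

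Part IA (five levels, one patient each, or three after a moderate toxicity) is closed to accrual. The number treated in it is not given.

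**The concern.** Section 9.2 says the size is whatever is needed to establish the MTD, so its range should follow from the escalation rules. It does not. Seven levels of up to six patients exceed 30 in Part IB alone, before Part IA patients and replacements are counted.

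The MTD is the primary objective. If 30 patients have been entered and the rule still calls for another cohort, Section 9 gives no instruction. The choice would then be made with toxicity data in hand: to amend, to stop short, or to name a recommended dose with fewer than six patients. Timing is affected too. At the Section 9.2 rate of 2 to 3 patients every 3 months, the 12 patients between 30 and 42 would take 12/3 × 3 = 12 to 12/2 × 3 = 18 months.

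**Working it through.** **Inputs.** Seven Part IB levels and 3 to 6 patients per level (Section 6.1.1). Escalation after 0/3 or 1/6 DLT, and at least six at the recommended dose (Section 6.2). Part IA by rule uses 1 to 5 × 3 = 15 patients (Section 6.1.1). The DLT probability per level is not given in the documents and is assumed below.

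**Step 1: try to reproduce 30.** Number of levels × 6 gives 4 × 6 = 24, 5 × 6 = 30, 6 × 6 = 36 and 7 × 6 = 42. Only five levels with no Part IA patients gives 30.

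**Step 2: count the current design.**

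- Through 7B with no DLT: 7 × 3 = 21.
- The same path with six at the recommended dose: 21 + 3 = 24.
- Maximum: 7 × 6 = 42, which is 12 above 30.
- With 1 to 3 Part IA patients: 25 to 27 on the no-DLT path and 43 to 45 at most.
- With an assumed 10% replacement rate: 24/0.9 gives 27 and 42/0.9 gives 47.

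If the three additional patients in Sections 6.3 and 9.1 are added to a level that already has six, the maximum is 42 + 3 = 45.

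**Step 3: room left under 30.** The no-DLT path leaves 30 − 24 = 6 places for Part IA, expansions and replacements together. With 1 to 3 Part IA patients, 3 to 5 places remain, so one level below 7B can be expanded. With 4 to 6, none can. With 7 or more, even the no-DLT path exceeds 30.

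**Step 4: chance of exceeding 30.** For DLT probability p at a level:

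- pass with three patients: (1 − p)³
- pass with six patients: 3p(1 − p)² × (1 − p)³
- otherwise escalation stops.

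At p = 0.10 these are 0.729 and 0.243 × 0.729 = 0.177. After stopping, or after passing 7B, the highest tolerated level is brought to six, stepping down if it then shows two or more DLTs. All paths were enumerated exactly, with no replacements. Part IB totals are multiples of three, so with 1 to 3 Part IA patients the overall total exceeds 30 exactly when Part IB needs 30 or more.

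| Assumed DLT rate, 1B to 7B | Expected Part IB number | P(total > 30), 1–3 Part IA patients |
|---|---|---|
| Flat 5% | 24.6 | 13.9% |
| Flat 10% | 22.0 | 20.8% |
| Flat 15% | 18.2 | 16.0% |
| Flat 20% | 14.6 | 8.9% |
| Flat 25% | 11.7 | 4% |
| Flat 30% | 9.6 | about 2% |
| Linear 5% to 20% | 23.0 | 20.1% |
| Linear 5% to 35% | 20.0 | 10.7% |
| Linear 10% to 40% | 17.1 | 6% |
| Linear 5% to 50% | 17.7 | 4% |
| 2, 3, 5, 8, 12, 20, 30% | 24.8 | 18.8% |

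The range is about 2–21%. The upper end is not sharp: a profile of 5, 5, 8, 10, 12, 18, 25% gives 21.7%. The chance peaks at low but non-zero rates, where escalation goes high with an occasional expansion. Replacements would raise every figure.

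**The case against.** The strongest reply is that 10–30 is a planning range and the escalation rule governs. That is largely right. A reader might infer that 30 patients cannot cover the design, or that the trial will run out of approved places. The documents support neither reading. The no-DLT path (24) fits within 30 if Part IA used six or fewer, and every expected Part IB number above is below 30. Section 9.2 calls the size planned and never calls 30 a cap.

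Several narrower objections also have force:

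- **42 is an extreme.** It needs one DLT in the first three patients and none in the next three at every level below 7B, and then an expansion at 7B. Its probability was at most about 0.02% in any scenario run, so planning below 42 is defensible if the shortfall is stated.
- **24 includes the top-up.** The row of the Section 6.2 table that requires six is written for a level below the maximally administered dose. Applying it at 7B after no DLTs is a reasonable reading, not explicit text.
- **A larger Part IA would raise the risk, but the text does not support assuming one.** With five Part IA patients, the flat 5%, 10% and 15% scenarios give 47%, 45% and 29%. However, Part IB starts at 75 mg once daily, below level 1A at 75 mg twice daily. This suggests that Part IA stopped early, and stopping at 1A uses 1 to 3 patients before replacements. The number is not stated, so this remains an inference.
- **The correlative analyses are not harmed.** The Section 9.4.1 detectable correlations reproduce: tanh[(1.960 + 0.842)/√(N − 3)] is 0.785 at N = 10 and 0.492 at N = 30, against the stated 0.79 and 0.49. More than 30 patients would only improve them.

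It is also tempting to say that 30 was carried over from a five-level Part IB, since 5 × 6 = 30 and Table 6 has five rows. The documents do not say so.

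What these replies leave standing is that 30 is the only upper figure in the plan, it is used for enrolment planning, and nothing links it to seven levels plus Part IA.

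**Conclusion.** The concern holds in a limited form. The planned size does not follow from the current Part IB and may not be enough to finish the escalation rule. The counts of 21, 24 and 42 come directly from the protocol's rules. The 2–21% chance of exceeding 30 rests on assumed DLT rates, 1 to 3 Part IA patients, no replacements, and the top-up and step-down reading in Step 4. On the same assumptions 30 is enough in roughly 79–98% of trials. This is a gap in the sample-size statement and in planning for an overrun. It is not a fault in the escalation rules.

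**What to change.** Amend Section 9.2 in one of two ways:

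1. State the number actually treated in Part IA plus the Part IB range, with a maximum of 42, the expected number under stated DLT assumptions, and a replacement allowance. If the three additional patients can be added to a level that already has six, say so and use 45.
2. Keep 30, give its chance of being exceeded under stated assumptions, and state what happens if it is reached before the MTD is defined.

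Update the planned enrolment table to match.

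Reconcile Table 6 (Section 7.1) with the schema in Section 6.1.1, because the number of levels drives the size. Table 6 has five rows, the last referring back to the schema. It lists 225 mg at 3B and 300 mg at 4B, where the schema lists 300 mg and 600 mg. Which is intended is for the sponsor to settle.

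The sample-size change costs one paragraph and one table in an amendment. The stated upper size may become larger, and the escalation decision rules do not change.

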9.3 Stratification Factors

N/A

9.4 Analysis of Secondary Endpoints

9.4.1 Correlative and exploratory biomarker analyses

Pre- to post-treatment changes in tissue biomarker levels measured on continuous and binary scales will be assessed using Wilcoxon signed rank or McNemar's tests, respectively (two-sided; $\alpha=0.05$). Associations between therapeutic response and baseline biomarker values or temporal changes in biomarkers will be explored using Fisher's exact tests or Wilcoxon rank sum tests. For the correlations between %IUDR-DNA incorporation and plasma PK, a two-sided Fisher's z-test with significance level of 0.05 and power of 80% will be used and the study will reject the null hypothesis (lack of correlation or $r_0=0$) if we observe a correlation with r ranging from 0.79 for $N=10$ subjects to 0.49 for $N=30$ subjects. For the correlation of %IUDR DNA incorporation in circulating granulocytes and peripheral blood counts and toxicities, assuming the target prevalence of grade 3/4 toxicity of 30%, the study will have a power of 80% with significance level of 0.05 on a two-sample means test to rule out the null hypothesis (equal means in groups with/ without grade 3/4 toxicity, $m_0=m_1$) if the observed mean %IUDR-DNA incorporation for patients with grade 3/4 toxicity is $m_1=3.3$ times the mean m_0 in the other group for $N=10$ enrolled subjects, and $m_1=2.1$ times the mean m_0 for $N=30$.

9.4.2 Determination of the pCR rate of IPdR + capecitabine + RT at the MTD

In rectal cancer, the absence of viable tumor cells in the resection specimen (primary tumor mass, surrounding tissue and lymph nodes, T0 N0 M0) at the time of surgery, termed pathologic complete response (pCR) (Ryan *et al.*, 2005; Martin *et al.*, 2012). pCR determination will be made by the pathologist at the treating institution.

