1.2 Secondary Objectives

- 1.2.1 To establish the pharmacokinetics (PK) of QD IPdR when combined with capecitabine.
- 1.2.2 To evaluate IUDR incorporation in circulating granulocytes and correlate these levels with IPdR plasma PK and clinical/laboratory toxicities.
- 1.2.3 To assess IUDR incorporation in tumor cells obtained from the surgical resection specimen and correlate IUDR incorporation in tumor cells with IPdR PK.
- 1.2.4 To assess IUDR incorporation in tumor cells obtained from the surgical resection specimen and correlate IUDR incorporation in tumor cells with tumor response as measured by pCR rate and Neoadjuvant Rectal (NAR) score.
- 1.2.5 To determine the pCR rate of IPdR + capecitabine + RT at the IPdR MTD as a measure of anti-tumor activity. Although the clinical benefit of IPdR has not yet been established, the intent of offering this treatment is to provide a possible therapeutic benefit, and thus the patient will be carefully monitored for tumor response and symptom relief in addition to safety and tolerability.
- 1.2.6 To determine the NAR score of IPdR + capecitabine + RT at the IPdR MTD.

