ACCORD 12/0405 PRODIGE 2 (Gerard et al. , 2010, Gerard et al. , 2012)	Primary endpoint: pCR (reported JCO 2010) Secondary endpoints: local recurrence rate, OS, DFS (reported JCO 2012)	2012	598	Cape + RT	13.9 %	Cape + RT + ox	19.2 %	.09
NSABP R-04 4 arm study cape vs 5FU \pm ox (O'Connell et al. , 2014, Allegra et al. , 2015)	Primary endpoints were all “surgical endpoints”: pCR, sphincter-sparing surgery, and surgical downstaging (conversion to sphincter-sparing surgery)	2014	1608	5FU or cape + RT	17.8 %	5FU or cape + RT + ox	19.5 %	.42
German CAO/ARO/AIO-04 (Rodel et al. , 2015)	Primary endpoint: DFS (reported 2015)	2015	1236	5FU + RT	13%	5FU + RT + ox	17%	.03

Trial	Endpoints	Year	N	Control Arm		Experimental Arm		p
				Treatment	pCR	Treatment	pCR	
2012, Rodel et al., 2015)	Secondary endpoints: pCR, toxicity, compliance (reported 2012)							
PETACC-6 (Haustermans et al., 2014, Schmoll et al., 2018)	Primary endpoint: DFS (reported 2018 JCO abstract only) Secondary endpoints: pCR, sphincter-sparing surgery, and surgical downstaging (conversion to sphincter-sparing surgery)	2014	1069	Cape + RT	11%	Cape + RT + ox	13%	.31
Jiao et al., 2015)	Primary endpoints: DFS, OS Secondary endpoints: pCR, toxicity, compliance	2015	206	Cape + RT	19%	Cape + RT + ox	23%	.49
FOWARC (Deng et al., 2016, Deng et al., 2019)	Primary endpoint: 3-year DFS Secondary endpoints: pCR, toxicity	2015	495	5FU + RT	14%	mFOLFOX6 + RT	27.5 %	.005

2.1.2 Pathologic complete response (pCR) as outcome measure in rectal cancer:

In rectal cancer, the absence of viable tumor cells in the resection specimen (primary tumor mass, surrounding tissue and lymph nodes) at the time of surgery, termed pathologic complete response (pCR), has been shown to correlate with improved outcome (Ryan *et al.*, 2005, Martin *et al.*, 2012). pCR is considered a standard endpoint for LARC clinical trials, although correlations of pCR with surgical results (*e.g.* extent of resection, sphincter preservation, downstaging) and OS are needed for definitive documentation of benefit. pCR rates for FP + RT vs. FP + RT + ox from recent phase 3 trials are presented in Table 1. In these 7 international, multi-institutional, randomized phase 3 trials, pCR was a primary or secondary endpoint in every trial.

2.1.3 Neoadjuvant Rectal Score (NAR score) as an outcome measure in rectal cancer:

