2.5.2 Capecitabine PK

Levels of capecitabine and its metabolites will be performed on Days 8, 21, and 35 in conjunction with the IPdR PK studies, using a portion of the 10-mL blood samples described above (Section 2.5.1).

Methodologies for the capecitabine PK analyses are those detailed and reported previously (Reigner *et al.*, 2001).

2.5.3 %IUDR-DNA cellular incorporation into tumor biopsy specimen

As the %IUDR-DNA cellular incorporation in human tumor xenografts in athymic mice was linearly related to the IPdR dose when given PO QD \times 6-14 days (Kinsella *et al.*, 1994; Kinsella *et al.*, 2000b; Seo *et al.*, 2004), we will evaluate for correlation between %IUDR-DNA cellular incorporation in tumor cells obtained from the surgical resection specimen and the dose of IPdR received as a biomarker of tumor radiosensitization. Evaluation for correlation of tumor response using pCR rate and NAR score and the %IUDR-DNA cellular incorporation in tumor cells obtained from the surgical resection specimen will also be performed.

2.5.4 %IUDR-DNA cellular incorporation in peripheral (circulating) granulocytes:

%IUDR-DNA cellular incorporation in peripheral (circulating) granulocytes will be performed as a biomarker of bone marrow acute normal tissue toxicity. These analyses will be performed at three time points on study, Days 8, 21, and 35. %IUDR-DNA cellular incorporation in peripheral (circulating) granulocytes will be correlated with peripheral blood counts, other systemic toxicities (CTCAE v5.0) and plasma PK obtained at the same time points. This assay was originally developed in [name]' laboratory at NCI (Belanger *et al.*, 1986; Belanger *et al.*, 1987).

Based on our pre-clinical data regarding %IUDR-DNA cellular incorporation in bone marrow

cells harvested directly from the femurs of athymic mice and ferrets following a 14 day exposure to PO QD IPdR (Kinsella *et al.*, 1994; Kinsella *et al.*, 2000; Seo *et al.*, 2004; Seo *et al.*, 2005) we would not expect a significant correlation between the %IUDR-DNA cellular incorporation in circulating granulocytes and PK measurements, peripheral blood counts, or systemic toxicities.

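### Tumor-cell IUDR cannot be related to pCR in a specimen that by definition holds no viable tumor cells, and Section 9.4.1 words detectable true correlations as observed rejection values

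*Combined protocol and SAP*

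**What the plan says.** **Tumor IUDR and response.** Objective 1.2.4 assesses IUDR in tumor cells from the surgical resection specimen in order to "correlate IUDR incorporation in tumor cells with tumor response as measured by pCR rate" and NAR score. Section 2.5.3 repeats this ("Evaluation for correlation of tumor response using pCR rate and NAR score"), and the tissue row of the Section 5.7 biomarker plan gives correlation with PK and clinical tumor response as the assay's purpose. Objective 1.2.3 correlates the same tumor measurement with IPdR PK. Section 2.1.2 defines pCR as "the absence of viable tumor cells in the resection specimen"; Sections 9.4.2 and 12.1.2 repeat the definition and add T0 N0 M0.

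**Correlation test.** Section 9.4.1 names a two-sided Fisher z-test for %IUDR-DNA incorporation against plasma PK, "with significance level of 0.05 and power of 80% will be used and the study will reject the null hypothesis" of zero correlation "if we observe a correlation with" r from 0.79 (N=10) to 0.49 (N=30). For granulocyte IUDR by toxicity group, it describes 80% power to reject equal means "if the observed mean %IUDR-DNA incorporation for patients with grade 3/4 toxicity is" 3.3 times (N=10) or 2.1 times (N=30) the mean of the other group. It gives no SD or CV.

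**Paired tissue tests.** The same section opens: "Pre- to post-treatment changes in tissue biomarker levels measured on continuous and binary scales will be assessed using Wilcoxon signed rank", with McNemar's test for binary measures. Sections 5.1 and 5.7 list one tissue specimen, the resection 8-12 weeks after treatment.

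**The concern.** The tumor-cell assay and the pCR outcome rest on the same specimen. Whenever the outcome is positive, the measurement is absent by definition. No sample size repairs that, so the pCR half of a secondary objective cannot be answered as written. The same absence reduces the N for tumor IUDR against NAR and against PK, while Section 9.2 refers readers to Section 9.4.1 for correlative power at up to 30 patients.

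The rejection rule as worded also disagrees with the test named in the same sentence. The r that a study can detect with 80% power is larger than the observed r at which its test becomes significant. A reader taking the wording at face value would treat a significant correlation between the two values as a failure to reject.

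**Working it through.** **1. Is there a tumor-IUDR value in a pCR patient?**

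- Objective 1.2.4 and Section 2.5.3 require tumor cells from the resection specimen.
- Sections 2.1.2, 9.4.2 and 12.1.2 define pCR as no viable tumor cells in that specimen.
- Sections 5.1 and 5.7 list no other tissue. The heading of Section 2.5.3 mentions a biopsy, but its text uses the resection specimen.
- Section 5.8.1.1 plans pathology QA of the tumor proportion but states no rule for a specimen without tumor.

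A pCR versus non-pCR comparison therefore has no values on the pCR side.

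**2. The plan's correlation figures.** Inputs from Section 9.4.1: two-sided alpha 0.05 (z = 1.960), power 80% (z = 0.842), N = 10 and 30.

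Detectable true r = tanh((1.960 + 0.842)/sqrt(N-3)); observed cut-off = tanh(1.960/sqrt(N-3)).

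| N | Stated r | Detectable true r | Observed cut-off |
|---|---|---|---|
| 10 | 0.79 | 0.785 | 0.630 |
| 30 | 0.49 | 0.492 | 0.360 |

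The stated figures reproduce as detectable true values. Power at a true r of 0.79 (N=10) is 80.9%, and at 0.49 (N=30) 79.5%. The t-test version of the cut-off is 0.632 and 0.361. A one-sided test would detect 0.735 and 0.445, which does not match the plan.

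**3. Tumor IUDR with tumor-free specimens removed.** Assumption: pCR between 11% and 27.5%, the lowest and highest rates in Table 1; the rate here may differ. Also assumed: every patient is resected and every non-pCR specimen is assayable, so these are best-case counts.

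- 11%: 10 × 0.89 = 8.9, about 9; 30 × 0.89 = 26.7, about 27.
- 27.5%: 10 × 0.725 = 7.25, about 7; 30 × 0.725 = 21.75, about 22.

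| Specimens | Detectable true r | Observed cut-off | Power at the stated true r |
|---|---|---|---|
| 9 of 10 | 0.816 | 0.664 | 75% (r = 0.79) |
| 7 of 10 | 0.886 | 0.753 | 57% (r = 0.79) |
| 27 of 30 | 0.517 | 0.380 | 75% (r = 0.49) |
| 22 of 30 | 0.567 | 0.422 | 65% (r = 0.49) |

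**4. Mean ratios.** A 30% prevalence of grade 3/4 toxicity gives 3 versus 7 (N=10) and 9 versus 21 (N=30). With the noncentral t, the standardized difference detectable with 80% power is 2.209 and 1.156. If the SD equals m0 (an assumption; the plan gives none), the detectable ratios are 1 + 2.209 = 3.21 and 1 + 1.156 = 2.16, close to the stated 3.3 and 2.1. Under the same assumption the observed-ratio cut-offs are about 2.6 and 1.8. So these ratios also look like true effects worded as observed ones.

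**5. A test for NAR.** The z-test in Section 9.4.1 is stated for PK only. Its sentence beginning "Associations between therapeutic response and baseline biomarker values" covers baseline values and changes over time; a single resection value is neither. No test is named for tumor IUDR against NAR.

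**The case against.** **The wording slip changes no planned analysis.** Section 9.4.1 names the test, its alpha and its power, and the figures are right as detectable effects. An analyst who runs that test gets a valid result. This stands. A reader might infer a true error rate of about 0.005 and power of about 50%, the values that follow if 0.79 and 0.49 are enforced as cut-offs. The documents do not support that, because it requires overriding the 0.05 and 80% stated in the same sentence.

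**The pCR rate could be read at group level, for example by dose level.** That avoids the patient-level comparison, but the IUDR values would still come only from specimens with residual tumor. Assaying whatever tissue remains in a pCR patient would measure non-tumor cells, which is not the stated objective.

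**The NAR half already refers to tumor cells, so its restriction is implicit.** Partly fair, but neither the condition nor the reduced N is stated. Nor would conditioning on non-pCR be correct: pCR also requires N0, so a pT0 N1 patient is non-pCR yet may have no tumor in the frozen piece. Assayable tumor is the right condition. Removing pCR patients also removes the lowest NAR scores, from which a reader might infer a biased correlation; nothing in the documents measures one.

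**The paired tissue tests look like leftover text.** Agreed. They cannot be run, but no listed objective depends on them.

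**The two mean ratios might seem to rest on different SDs.** A normal approximation implies 1.19 and 0.99 times m0, but with three patients in one group it is poor. The t version gives 1.04 and 0.95, so inconsistency is not shown. The missing SD is a small reporting gap.

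**Conclusion.** The point holds in two parts and should be corrected.

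The more substantive part is that the pCR half of objective 1.2.4 cannot be answered from the resection specimen. Tumor IUDR against NAR and against PK is limited to specimens with assayable tumor. Under the assumed pCR range, that is at best 7-9 of 10 or 22-27 of 30, with detectable true r of 0.82-0.89 or 0.52-0.57 instead of 0.79 or 0.49. These sizes rest on the Table 1 rates and on every non-pCR specimen being usable.

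The second part is certain but editorial: 0.79 and 0.49 are true r detectable with 80% power, and the named test rejects at observed |r| of about 0.63 and 0.36. The mean-ratio wording and the paired tissue tests are minor.

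Nothing here touches the MTD, dose escalation or the granulocyte-PK detectable r. The calendar's Day 21 and Day 35 draws fall on Sundays (radiation runs Monday to Friday on Days 15-19 and 29-33), while Sections 5.2.2 and 5.6.1 set Monday-to-Thursday collection for fresh blood. That is a separate matter to reconcile.

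**What to change.** 1. Remove the tumor-IUDR-versus-pCR comparison from objective 1.2.4 and Section 2.5.3, and align the tissue purpose in Section 5.7.
2. Limit tumor IUDR versus NAR, and versus PK (objective 1.2.3), to specimens in which the Section 5.8.1.1 pathology QA confirms tumor. Label the results as conditional on assayable residual tumor, name a rank correlation for NAR, and restate the detectable r for the reduced N with the assumed pCR range shown.
3. Reword Section 9.4.1 to say that the study has 80% power for a true r of 0.79 (N=10) or 0.49 (N=30), and that the null is rejected at two-sided p<0.05, which corresponds to an observed |r| above about 0.63 or 0.36. Call 3.3 and 2.1 true mean ratios and state the SD behind them.
4. Delete the paired pre/post tissue tests.

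The cost is a text amendment to objectives 1.2.3 and 1.2.4 and Sections 2.5.3, 5.7 and 9.4.1, with no new samples or visits. The downside is that the pCR correlation is given up and the tumor-IUDR analyses are stated with lower power.
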